Planned enrolment	3 municipalities and 9 municipality districts

Sample size estimation

The required sample size calculated before recruitment of participants aimed to detect a difference of 7 h/week for the primary outcome RUD. Based on the literature[4], we assumed that the number of hours of informal care is 46 h/week with a standard deviation (SD) of 20 h/week. With 80% power and a significance level of 5%, the required sample size was estimated to be 260 dyads. To allow for 20% loss to follow-up, a total of 315 dyads, equaling 105 per municipality, must be included.

The post-hoc sample size calculations based on the outcome PADL showed that by treating the study as an individually randomized stepped wedge design[3], with 3 intervention sequences, 5 periods, effect size of 7h/week, outcome variance of 400, significance level of 5% and within-individual correlation of 0.1075 over the 24 month trial would require a total of 240 dyads to be included. To allow for 20% loss to follow-up, the sample size must reach 288 dyads.

Randomization, blinding and unblinding procedures

Block randomization was performed using a computerized random number generator to allocate individual dyads to the three intervention sequences. We will apply stratification to secure that about one third of the dyads in each treatment sequence will be recruited from each municipality. Research assistants, researchers conducting the analyses and other study personal conducting data collection will be blinded to the randomization order, the dyads will be blinded to group allocation until contacted by their coordinator at start of the intervention period. Given the practice change of the intervention, the municipality home care services and coordinators will be informed about allocation sequence when their clusters entered the intervention period.

Analysis Sets

Full Analysis Set (FAS)

The intention-to-treat population includes all randomized dyads who were assigned a coordinator by the municipality. The dyads will be analyzed separately (i.e., PwD and caregiver), dependent on outcome of interest.

This will be the primary analysis set for baseline summary statistics of demographics, primary, secondary and exploratory efficacy analysis as elaborated in section 10.

Municipal coordinator set (MCS)

All coordinators in all municipality districts

Usage overview of analysis sets table

Analyses	FAS	MCS	
Disposition			
Demographics and background	x		
Medical history			

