Efficacy: primary	x		
Efficacy: secondary	x		x
Efficacy: other	x	x	x

General Statistical Methods and Definitions

General statistical methods

The statistical analysis will be presented by treatment group for the different analysis sets as outlined in section 4.

Stepped wedge design (SWD) do not strictly feature a treatment and control group, and thus, the summary statistics will include all participants at baseline, and the characteristics according to intervention sequences.

Continuous variables will be summarized using descriptive statistics (means and interquartile ranges), and categorical variables will be presented by frequencies and percentages. A table will present the number of caregivers and PwD with the following data: missing values, mean, median, standard deviation and confidence intervals.

Means and median as well as percentages will be presented with 1 additional decimal place and standard deviation by 2 additional decimals.

If the number of PwD or caregivers in a category is 0, then percentage will not be displayed.

P-values will be reported to 3 decimal places.

Unless otherwise specified, all statistical tests will be two-sided.

Causal model

Due to the longitudinal structure of the collected trial data, we considered the following linear mixed model to estimate and identify the treatment effect due to the intervention. Our SWD, consisting of $j = 3$ municipalities and 3 steps, is a closed cohort design, and thus, time related confounders are important to adjust for [5] when assessing treatment effect.

Mixed-effects regression is one of the most common approaches when estimating the intervention effect in SWD [6, 7]. In our design, we will consider the following model as our primary analysis model, assuming a constant treatment effect.

$$(1) Y_{ijt} = \beta_0 + O_{ijt}\beta_1 + X_{ijt}\beta_2 + b_i + \epsilon_{ijt}$$

where notation Y_{ijt} refers to the primary outcome caregiver burden (RUD and RSS), elaborated in section 3 Study Design, for individual i nested in municipality j at time point t . O_{ijt} is the treatment indicator (effect of receiving assistance from a municipality coordinator) and β_1 is the average treatment effect parameter of interest. Since the study collects repeated observations from the same participants, we consider a longitudinal regression model that adjusts for participant-level random effect, $b_i \sim N(0, \sigma_b^2)$, which corresponds to a compound symmetric correlation structure.

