$\epsilon_{ijt} \sim N(0, \sigma_\epsilon^2)$ represents random error that changes across t and i .

X_{ijt} constitutes control variables which are demographic, socio-economic and clinical confounders (age, sex, caregiver marital status, work status, ADL function), and stratification variables used in the design stage.

Due to the non-normal distribution of hours and costs we will use both linear mixed-effects, as well as general lineal mixed regression model for assessing both primary variables. For RSS, and other continuous variables, we use Linear Mixed regression model. Log-transformation of the outcome will also be considered to address potential non-normality in the response.

Intervention effect

In secondary analysis, we will further examine the extent to which the treatment effect will depend on the calendar time when COVID lockdown happened, and the potential for delayed effect. We collectively refer these effects as heterogeneous treatment effect, and provide a schematic illustration following Section 3.2 of Li et al. (2020) [6]. The rationale is that there the lockdown during the pandemic may contribute to change in the intervention effect. In addition, the intervention may be most effective when it is first introduced, and the sustained effect may be smaller. Therefore, when modelling the intervention effect, we will allow for heterogeneous effect and assess the robustness of our primary analysis. The table below shows how the intervention effect can differ between periods (t) across different groups (g). The deltas (δ) constitute the intervention effect, and their subscript defines heterogeneous effects where δ_0 is the pre-lockdown intervention effect, δ_0^* is the intervention effect post-lockdown, and δ_1^* is the follow-up post-lockdown treatment effect.

When modelling the intervention effect, we will test the null-hypothesis (H_0)

$$\delta_0 = \delta_0^* = \delta_1^*$$

	$t = 1$	$t = 2$	$t = 3$	$t = 4$
$g = 3$			δ_0^*	δ_1^*
$g = 2$		δ_0^*	δ_1^*	δ_1^*
$g = 1$	δ_0	δ_1^*	δ_1^*	δ_1^*

Economic evaluation

If we identify an average treatment effect on one of the primary and secondary outcomes, we will use cost-efficiency (CEA) and cost-utility analysis (CUA) to evaluate the economic effects of the LIVE treatment.

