- Formal caregiver (whether dyads are receiving care by home nursing)
- Categories of caregiver burden intensity
- Categories of dementia diagnoses

Results from subgroups will be presented for the primary analyses.

Observation and analysis times

Study periods

Timeline															
Groups/participants	Inclusion period	Control group			Kristiansand 3, N=35			Bærum 3, N=35			Bergen 3, N=35				
					Kristiansand 2, N=35										
					Bærum 2, N=35										
					Bergen 2, N=35										
		Kristiansand 1, N=35						Follow up							
Number of months		0	1 2	3 4	5 6	7 8	9 10	11 12	13 14	15 16	17 18	19 20	21 22	23 24	
Date		01.09 2019		01.03 2020		01.09 2020		01.03 2021							

		STUDY PERIOD							
		Enrollment		Allocation	Post-allocation				Close-out
TIMEPOINT	-t	0		t1	t2	t3	t4	t5	
ENROLLMENT:									
Eligibilityscreen	x								
Informed consent	x								
Allocation		x							
INTERVENTIONS:									
1st group			x	x					
2nd group				x	x				
3rd group					x	x			
ASSESSMENTS:									
Baseline variables			x						
Outcome variables				x	x	x	x	x	

The stepped wedge randomized control design. A) The randomization in time takes place at month 0. First group (red) is in the intervention period from month 1 to 6, second group (yellow) from month 7 to 12, third group (green) from month 13 to 18. Implementation seminars will be held at month 0, 6 and 12, midway evaluation at month 3, 9 and 15. Data will be collected at baseline (month 0), after first intervention period (month 6-7), after second intervention period (month 12-13), after third intervention period (month 18-19) and at end of study at 24 months. B) Schedule of enrollment, interventions and assessments over the study period.

Demographics and Background Characteristics

Demographics and baseline characteristics

The following demographic characteristics will be presented descriptively and listed for both PwD and caregiver:

- Sex (male, female)
- Age in years
- Marital status (spouse, child)
- Work status (employed, unemployed, retired)
- Number of co-caregivers
- MMSE total score
- RUD (number of care hours the last 30 days)
- RSS total score
- NPI total score
- QoL total score

Date of informed consent and protocol version will be listed

Medical history

We will provide information on the number of years since formal diagnosis of dementia together with descriptive statistics.

Exposure and Compliance

Treatment groups

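### The primary model fixes equal within-person correlation and constant variance over 24 months and names no robust variance, so intervals are mis-sized if correlation decays; the error is modest once period effects are fitted

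*SAP*

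**What the plan says.** The SAP's Causal model section introduces equation (1) with the words "we will consider the following model as our primary analysis model, assuming a constant treatment effect". The equation has an intercept, a treatment indicator, covariates, one participant random intercept and a residual. The random intercept is described as one "which corresponds to a compound symmetric correlation structure". The residual is normal with a single variance and "represents random error that changes across t and i"; no serial correlation is attached to it.

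The covariates are listed as "age, sex, caregiver marital status, work status, ADL function), and stratification variables used in the design stage". No period term appears in the equation or in that list, although the same section says that "time related confounders are important to adjust for".

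Under Study periods, outcomes are collected at baseline, months 6-7 and 12-13, "after third intervention period (month 18-19) and at end of study at 24 months", which makes five occasions. The post-hoc calculation under Sample size estimation uses a "within-individual correlation of 0.1075 over the 24 month trial" and does not say to which time lag it belongs.

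The SAP also says that "Due to the non-normal distribution of hours and costs" a second type of mixed regression will be used, and that log-transformation will be considered. The Missing data section relies on covariate adjustment under missing at random. The section on sensitivity and robustness tests names subgroups, item-level analyses and a cost simulation.

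**The concern.** A random intercept with an independent residual says that a caregiver's months 0 and 24 are as strongly correlated as months 0 and 6, with the same spread throughout. Over two years of a progressive disease, fading correlation is at least plausible. If it fades, the standard error computed from the fitted model is not the true one, and the primary intervals and p-values take the wrong width.

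Nothing in the plan guards against this. The second mixed regression and the log-transformation deal with the shape of the distribution. The heterogeneous-effect model under Intervention effect deals with the mean. The listed robustness checks do not touch the correlation structure or the variance estimator.

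**Working it through.** **Inputs from the SAP.** 3 sequences, 5 occasions, variance 400 (SD 20), effect 7 h/week, within-individual correlation 0.1075, 315 dyads (105 per sequence). The treatment indicator stays on once started, as in the table under Intervention effect. **Assumptions.** The decay shape and rates (the SAP gives none), no dropout, and no time trend unless stated.

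**The plan's own figures.** Two-group size: 2 × (1.960 + 0.842)² × 400/49 = 128.1, so 129 per arm and 258 in total. The t-based version gives 130 per arm, the stated 260. For the post-hoc size, the variance of the treatment estimate under equal correlation 0.1075 with period effects and one dyad per sequence is about 301.8. N = 3 × 301.8 × (z_α + z_power)²/49 gives 145 at 80% power, 194 at 90% and 240 at 95%. The stated 240 is thus reproduced with period effects and equal correlation, at a power that the SAP does not state.

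**Method.** Let V be the true covariance, S the covariance that the random-intercept model settles on, and X the design.

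- A = (Σ X′S⁻¹X)⁻¹ and B = Σ X′S⁻¹VS⁻¹X, summed over dyads
- model SE = √A₁₁; true SE = √(ABA)₁₁; q = model SE / true SE
- two-sided type I error = 2Φ(−1.96q)

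The model settles on the average of the ten pairwise correlations. If 0.1075 is the 24-month value under first-order decay, the 6-month value is 0.1075^(1/4) = 0.573, and the fitted value is (4 × 0.573 + 3 × 0.328 + 2 × 0.188 + 0.1075)/10 = 0.376.

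**Results, 105 dyads per sequence.**

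| 6-month correlation | q, no period term | type I | q, period effects | type I |
|---|---|---|---|---|
| equal, 0.1075 | 1.00 | 5.0% | 1.00 | 5.0% |
| decay, 0.1075 | 0.95 | 6.2% | 0.99 | 5.3% |
| decay, 0.3 | 0.88 | 8.5% | 0.98 | 5.6% |
| decay, 0.5 | 0.82 | 11.0% | 0.99 | 5.2% |
| decay, 0.573 | 0.80 | 11.9% | 1.00 | 4.9% |
| decay, 0.7 | 0.77 | 13.4% | 1.04 | 4.2% |
| decay, 0.8 | 0.74 | 14.5% | 1.07 | 3.5% |
| decay, 0.9 | 0.72 | 15.6% | 1.12 | 2.8% |

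For 0.573 without a period term, the model SE is 0.849 and the true SE 1.067, so q = 0.849/1.067 = 0.80.

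**Simulation check.** Simulations of 2,000 null trials per case at 80 dyads per sequence agree closely. They also covered random-slope truths, where variance changes over time: q was 1.11-1.19 with period effects and 0.81-0.89 without. Clustered robust standard errors gave 4.4% to 5.6% type I error in every case, with or without period effects.

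**What robust errors cannot do.** Add an assumed trend of 1 h/week per 6-month period, with decay at 0.573 and no period term. The treatment estimate is then biased by 2.42 h/week. With the correct SE, 2.42/1.067 = 2.27 and the rejection rate is Φ(2.27 − 1.96) = 62%. With the model SE it is Φ((2.42 − 1.96 × 0.850)/1.067) = 76%. With period effects the bias is zero and both rates are 5%.

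**The case against.** The strongest reply is that the large figures belong to a different fault. A type I error of 11% to 16% appears only without period terms. The SAP calls adjustment for time important, so the intended model may well contain time, and then coverage is 94.4% to 97.2% across the decays tried. This stands, and it limits the size of the point. It does not remove the point: the printed equation has no period term, and the excess in the table arises with no time trend at all, so it comes from the correlation structure and not from confounding by time.

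A second reply is that 0.1075 need not be a 24-month value. This also stands. Read as an equal correlation, it gives no distortion; read as a 6-month value, it gives 6.2% without and 5.3% with period effects. Pure first-order decay is a harsh case as well: truths that mix measurement noise with slower decay gave q between 0.83 and 0.96 without period terms.

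A third reply is that the SAP nowhere says its standard errors are model-based. Correct: it is silent on the variance estimator. A reader might infer that it rules robust errors out, but the text supports only that none is requested.

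Finally, the SAP's remark on non-normal hours and costs is not evidence for this point. The plan already answers it with a second model and a possible transformation.

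**Conclusion.** The point holds in a limited form. The primary model fixes one correlation and one variance over 24 months and names no safeguard, so interval width depends on an unchecked assumption. With period effects, the standard error is between about 2% too small and 12% too large over 6-month correlations of 0.1075 to 0.9, and the larger error costs power rather than validity. With equation (1) as printed and no trend, standard errors are 5% to 28% too small and type I error is 6% to 16%. Under equal correlation there is no error. All of this rests on assumed decay.

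A reader might infer that the primary p-values carry a type I error of 11% to 15% and that robust standard errors alone would restore 5%. The documents do not support either step. The SAP gives no decay rate and no lag for 0.1075, and the higher figures need both the missing period term and an absent time trend. With a trend, the printed model is biased, and no variance estimator repairs that. The missing period term is the larger, separate fault.

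**What to change.** In the Causal model section, specify standard errors clustered on the dyad for all mixed-model estimates (in Stata, `mixed` with `vce(cluster dyad)`), fitted together with fixed effects for assessment period. The two must go together, because robust errors do not remove time-trend bias.

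In the sensitivity section, add a refit of the primary model with an autoregressive residual in place of the equal-correlation structure. The SAP allows 20% loss to follow-up and relies on missing at random. Under such dropout, a wrong correlation structure can shift the estimate itself, and robust errors do not protect against that.

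Possible wording: *Mixed-model estimates will include fixed effects for period and will be reported with dyad-clustered robust standard errors; a sensitivity analysis will use a first-order autoregressive residual.*

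The cost is one code option, one SAP sentence and one further model fit, besides the period terms. With about 300 dyads as clusters, no small-sample problem is expected.

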Primary objective	To determine treatment effect on caregiver burden measured as Resource Utilization Dementia (RUD), and the Relative Stress Scale (RSS). Based on the correlation coefficient, we will use all three subcategories of RUD separately. Total score will be used when assessing RSS. Further, we will evaluate the economic consequences of the treatment by calculating Incremental Cost-Effectiveness Ratio (ICER) and quality adjusted life years (QALY).
Secondary objectives	To determine treatment effect on quality of life (QoL) using the European Quality of Life – 5 dimension – 5 levels (EQ-5D-5L), EQ-5D-VAS scale, Quality of Life in Alzheimer's disease scale (QoL-AD); neuropsychiatric symptoms in dementia using the Neuropsychiatric Inventory 12 item (NPI-12), agitation in dementia using Cohen-Mansfield Agitation Inventory (CMAI), depression in old age (Geriatric Depression Scale - GDS), functional level for instrumental and personal activities (ADL and IADL), and the caregiver rating of clinical meaningful change using Clinical Global Impression of Change (CGIC).
Exploratory objectives	
In line with total score of RSS, we will also explore the treatment effect on both single and clustered items.
 
In line with total score of QoL based instruments (EQ-5D-5L, QoL-AD, QoL – CG, GDS), we will also explore the treatment effect on both single and clustered items
 
To assess the effect on pain in dementia using the Mobilization – Observation – Behavior – Intensity Dementia Pain Scale (MOBID-2)
 
To determine the characteristics of the dyads who had the highest improvement in RUD and RSS, i.e., those who benefitted the most from the intervention.

Endpoints	
Primary endpoint: Change in caregiver burden and informal care time among the caregivers in the intervention group during active intervention period, and the follow-up. Change in Cost-efficiency of treatment.
 
Secondary endpoint: Improvement in QoL for both PwD and caregivers. Reduction in neuropsychiatric symptoms in dementia and functional level during active intervention period and follow-up.
 
Exploratory endpoint: Reduction in pain during active intervention period.

Treatments	Allocation to municipal coordinator delivering the multicomponent LIVE intervention (L:learning, I: innovation, V: volunteering and E:empowerment) or care as usual.
Number of patients	315 dyads will be screened to achieve at least 105 dyads per municipality.

Safety analysis	Not applicable

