In cost-effectiveness analysis the effect is measured in health units (or other outcome measures depending on the context). The outcomes are common health measures in natural units, and the results are presented as cost per effect unit/outcome measure. In cost-utility analysis, also called cost per QALY analysis, the effect is measured as quality-adjusted life years (QALYs) on a scale of 0 (death) and 1 (full health). A quality-adjusted life year (QALY) captures both life years gained and improved health as a result of treatment [8, 9].

The economic evaluation will be measured at society level.

Costs and QALYs will be measured for each phase of 6 months

The cost-effective analysis will relate the difference in total mean costs at societal level per 6 months between all intervention -and usual care phases to the difference in RUD, RSS, QoLs, QALYs, NPI, function level such as ADL and IADL

The analysis will use a discounting rate at 3.5%.

Following other costs studies calculating RUD in an advanced economy setting, our analysis will use 35% of the Norwegian average income to value lost leisure time for retired caregiver.

The primary economic evaluation will use the opportunity cost method to assess the costs of informal caregiving. For a sensitivity analysis, the replacement cost will be used.

Unit costs will be based on information from Statistics Norway and information from the primary health care institutions in each municipalities.

Covariates and strata

In the main statistical analyses, the following covariates are used for both caregivers and PwD.

For PwD: Age, sex, marital status, cohabitation status, number of co-caregivers, clinical characteristics of dementia (dementia etiology, neuropsychiatric symptoms, functional level)

For Caregivers: Age, sex, marital status, cohabitation status, numbers of co-caregivers involved in caregiving for the PwD, work status, use of health care services,

Groups, municipalities

Municipalities will be grouped in the main analysis and used as an adjustment variable (fixed effects). This is not the case for district municipalities as we consider that the dyads are similar within municipalities

Subgroups

In subgroup analyses, the following covariates will be used to define relevant subgroups:

- Gender (male, female)
- Work (retired and working caregivers)
- Caregiver relation (spouse, children)
- Residency (living alone, or with caregiver)

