The definition of treatment assignment as specified in section “Analysis sets” will be used in this section, too.

Deviations from the randomized treatment sequence occurred under the first Covid-19 lockdown, see section Modification History, Changes to the study protocol

Treatment duration

Each municipal coordinators are writing logs, and we will collect the data and calculate total hours of care by the coordinator, divided into different categories.

Descriptive statistics for the total hours of care by the coordinators will be presented.

Delivery of the intervention

One coordinator from the municipal per dyad

Efficacy

Primary efficacy analysis

The primary efficacy analysis variable caregiver burden is based on two variables. The first is RUD, divided in three categories: number of hours the last 30 days invested in personal, instrumental and supervisory care. The second is RSS measured as total score but also

specific and clustered items. Lower hours of informal care as well as lower score of RSS, indicates reduction in caregiver burden.

The null hypothesis states that there are no differences in burden and resource utilization between the LIVE intervention and usual care. The primary alternative hypothesis (H1) states that the LIVE intervention will improve caregiver burden and resource utilization compared with usual care. The secondary alternative hypothesis (H2) is that the LIVE intervention will provide more cost-efficient services than usual care.

H0: LIVE treatment = control

H1: LIVE treatment > control

H2: cost efficiency > control

where LIVE treatment denotes the proportion of caregivers experiencing improvement in care burden. The primary hypothesis will be statistically assessed by means of a χ^2 test on the one-sided significance level of 2.5% (corresponding to 5% two-sided).

We will plot the regression line to visualize the parallel effect for both treatment group and control group.

The significance level will be set to 2.5% (one-sided, corresponding to 5% two-sided), the corresponding level of one-sided CI is 97.5% (corresponding to 95% two-sided).

Missing data

We will pre-specify a list of baseline covariates that are likely associated with the missingness and the outcome, and adjust for these covariates in our primary analyses. This covariate-adjusted analysis will be valid under the missing at random (MAR) mechanism.

Sensitivity and robustness tests of regression analyses and economic evaluation

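### The primary model indexes its covariates by visit and does not limit ADL function, neuropsychiatric symptoms or service use to baseline, so it allows adjustment for post-crossover values of the trial's own outcomes

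*SAP*

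**What the plan says.** **Primary model.** The Causal model section gives equation (1) as the primary analysis model and makes β1 the average treatment effect. The outcome is that of an individual "nested in municipality j at time point t". The covariates are written X_ijt, with the same time index. That vector "constitutes control variables which are demographic, socio-economic and clinical confounders (age, sex, caregiver marital status, work status, ADL function", together with the stratification variables. Equation (1) as printed has no separate term for visit or period.

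**Main-analysis lists.** The Covariates and strata section opens with: "In the main statistical analyses, the following covariates are used for both caregivers and PwD". For the person with dementia the list includes "clinical characteristics of dementia (dementia etiology, neuropsychiatric symptoms, functional level". For the caregiver it includes "numbers of co-caregivers involved in caregiving for the PwD, work status, use of health care services". Neither list says when the variables are measured.

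**The same variables as outcomes.** The secondary objectives in the Study Design table include NPI-12 and "functional level for instrumental and personal activities (ADL and IADL". The secondary endpoint reads: "Reduction in neuropsychiatric symptoms in dementia and functional level during active intervention period and follow-up".

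**Baseline covariates.** The Missing data section says that a list of baseline covariates related to missingness and outcome will be specified and adjusted for in the primary analyses. The list is not given, and the section does not refer to either of the other two.

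**The concern.** The primary objective asks for the effect of LIVE on caregiver burden, which means the total effect by whatever route. If function or symptoms at a visit after crossover have been changed by the intervention, adjusting for them blocks that route, and β1 becomes a direct effect. If unmeasured disease progression drives both the covariate and the burden, the adjustment can add further bias.

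ADL function matters most. One primary outcome is hours of personal, instrumental and supervisory care, and the need for such care depends closely on function. An intervention that works partly through function or symptoms could then look weaker than it is. The plan gives three covariate statements and no measurement time for these variables in the two lists that name them, so the choice would fall to the analyst.

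**Working it through.** **1. Reproduce the plan's figure.** Inputs from Sample size estimation: difference 7 h/week, SD 20 h/week, power 80%, significance level 5% (taken as two-sided).

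n per group = 2 × (1.960 + 0.842)² × 20² / 7² = 128.1, so 129 per group and 258 in total. The t-based version gives 130 per group, or 260, which is the stated number. The point below does not challenge this figure.

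**2. Set the statements on covariate timing side by side.**

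| SAP section | Variables | Timing |
|---|---|---|
| Causal model | ADL function and others | index t; no limit to baseline |
| Covariates and strata | neuropsychiatric symptoms, functional level, service use and others | none stated |
| Missing data | not listed | baseline |

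Outcome data are collected at month 0, months 6–7, 12–13 and 18–19, and month 24, so visit-level ADL and NPI values would exist. Nothing in the first two rows prevents their use.

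**3. Effect of visit-level adjustment.** Let m be the share of the effect that passes through the adjusted variables. The SAP gives no value, so m is an assumption. The adjusted coefficient is about 7 × (1 − m). Power uses a simple two-group comparison with 130 per group: Φ(δ / (20 × √(2/130)) − 1.96), where 20 × √(2/130) = 2.481.

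| m | δ (h/week) | Power at 260 dyads |
|---|---|---|
| 0 | 7.0 | 0.81 |
| 25% | 5.25 | 0.56 |
| 50% | 3.5 | 0.29 |

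The power column only shows scale; it is not the power of the stepped-wedge analysis. In a simulated stepped wedge with three sequences and five visits, a true effect of −7 and no disease progression, visit-level adjustment gave about −5.2 and −3.4 for m = 25% and 50%. Month-0 adjustment gave about −7.

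**4. Does month-0 adjustment alone suffice?** Assumptions: exposure stays on from the first visit after crossover, as in the constant-effect model; the within-individual correlation is 0.1075 and the variance 400, both from the SAP's post-hoc sample size calculation; disease progression adds c h/week of care per period. The value of c is assumed.

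The three sequences have exposure rows (0,1,1,1,1), (0,0,1,1,1) and (0,0,0,1,1). The expected generalised least squares estimate is (ΣX′V⁻¹X)⁻¹ ΣX′V⁻¹E(Y), with E(Y) = 46 − 7 × exposure + c × (visit number − 1). A month-0 covariate is the same at every visit and balanced across sequences by randomisation, so it does not change these expectations.

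| c (h/week per period) | Without visit effects | With visit effects |
|---|---|---|
| 0 | −7.0 | −7.0 |
| 1 | −4.7 | −7.0 |
| 2 | −2.4 | −7.0 |

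Without visit effects, each 1 h/week of progression per period moves the estimate by about 2.3 h/week towards zero. In simulations where progression acts wholly through ADL, visit-level ADL absorbs that trend but still loses the mediated share (about −5.3 and −3.5 at m = 25% and 50%). Only month-0 covariates with visit effects recovered about −7 in every scenario.

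**The case against.** **Visit-level use is inferred.** The vector X_ijt also holds sex and the stratification variables, so its subscript does not prove that ADL varies by visit. The only explicit statement on covariate timing, under Missing data, says baseline. This stands, and it rules out saying that the plan adjusts for post-crossover values. It does not remove the problem, because that statement names no variables and is not linked to the lists that do.

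**Service use as a target.** A reader might infer that coordinators work mainly by changing the services a dyad uses. The SAP does not say so. H1 "states that the LIVE intervention will improve caregiver burden and resource utilization compared with usual care", but resource utilization there sits beside RUD, which that section defines as informal care hours. Formal service use is not a listed objective. The argument rests on ADL and NPI; service use is only another changeable covariate with no stated timing.

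**Outcome on both sides.** A reader might also infer that the ADL and NPI analyses would contain their own outcome as a covariate. The SAP defines equation (1) for the primary outcome and does not say that the main-analysis lists apply unchanged to secondary models.

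**Randomisation is not enough by itself.** It is tempting to argue that ADL cannot confound because crossover order is randomised. In a stepped wedge, exposure rises with calendar time, and randomisation protects the estimate only within periods. With no period term in equation (1), declining function is associated with exposure. The SAP also reports departures from the randomised sequence under the first lockdown. This objection stands and changes the remedy: month-0 covariates alone can leave the estimate further from the truth than visit-level ones.

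**Circular magnitude.** The attenuation restates the assumed m. That is correct, and the figures serve only as illustration.

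**Conclusion.** The concern holds as a defect in how the primary model is fixed. As written, equation (1) and the main-analysis lists allow post-crossover values of variables that the trial itself treats as outcomes. If such values are used and the intervention changes them, β1 is no longer the total effect that the primary objective asks about. Whether this will happen is not settled by the SAP.

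The direction, towards zero, assumes that the mediated part acts in the same direction as the rest. The size cannot be derived from the document: 7 h/week falling to about 5.3 or 3.5 depends wholly on assumed shares of 25% or 50%. The companion result, that month-0 covariates without visit effects give about −4.7 or −2.4 instead of −7, depends on assumed progression of 1 or 2 h/week per period. A reader should not conclude that the planned analysis is certain to lose part of the effect. The conclusion is that the plan leaves open a choice that can change the estimand, and this should be closed before analysis.

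**What to change.** - State that ADL function, neuropsychiatric symptoms, use of health care services and every other changeable covariate (such as work status, cohabitation and number of co-caregivers) enter the primary and secondary models at month-0 values only. Write the vector without the time index.
- In the same revision, add categorical visit (period) fixed effects to equation (1). The two changes should not be separated.
- Replace the covariate statements under Causal model, Covariates and strata, and Missing data with one named list for each outcome.
- Report any visit-level adjustment only as a labelled exploratory mediation or sensitivity analysis.

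The cost is small. Month-0 data collection is already in the schedule, and the stated sample size target is unchanged. Month-0 covariates explain slightly less residual variance than visit-level ones, and the visit effects use a few degrees of freedom (four for five visits).
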